Listening effort and fatigue	FAS total score, EAS total score, LEQ-CI* total score at 1, 3, 6, and 9 months. Scores will be calculated using the algorithms in the questionnaire manuals.
Tinnitus severity	Global 25-item TFI score Global 19-item TFI score (excluding sleep and auditory subscales) TFI scores for 8 subscales All at 1, 3, 6, and 9 months.
Tinnitus loudness	
 • VAS-L rating. Participants mark the loudness of their tinnitus at any point along the numerical scale, with word descriptors utilised as anchor points at 0 for “extremely weak,” 30 for “moderate,” 50 for “strong,” 70 for “very strong,” and 100 for “extremely strong” tinnitus loudness. 
Immediately before and after first treatment activation, and at 1, 3, 6, and 9 months.

Mood	HADS anxiety and depression subscale scores at 1, 3, 6, and 9 months.
Hearing-specific quality of life	NCIQ total and six subdomain scores YBHRQL binaural utility value HHIA total score and two subscale (emotional and social/situational) scores All at 1 month, 3 months, 6 months, and 9 months.
Health-related quality of life	HUI3 multi-attribute utility value, EQ-5D-5L health utility value using EQ-5D-3L UK value set ICECAP-A tariff value All at 1 month, 3 months, 6 months, and 9 months.
Global ratings of change	Likert scale ratings of change (7 points from much worse to much improved) in hearing and quality of life relative to two anchor points (immediately prior to first treatment activation; since the last trial appointment) at 1, 3, 6, and 9 months.
Audiometric thresholds	Unaided audiometric thresholds at first treatment activation and at 3, 6 and 9 months.

Outcome Measure	Derivation
	Aided audiometric thresholds at first treatment activation and at 3 and 9 months.

*Data only to be collected using LEQ-CI questionnaire once licence is in place

Assessment of safety

Safety data, including number of expected AEs and SAEs and unexpected related SAEs will be summarised with descriptive statistics according to the treatment the participant received, irrespective of randomisation; where anyone received more than one treatment (e.g., HA then CI) these will be summarised separately. Where a participant did not receive their allocated treatment but had an expected AE, or SAE this will be indicated.

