4. disease or disorder being studied, or sign or symptom associated with the disease or disorder unless more severe than expected for the participant's condition.
5. overdose of concurrent medication without any signs or symptoms.
6. expected AE as listed below.

Expected adverse events

The treatments provided to both intervention arms are widely available within the NHS, used in standard care and considered to be safe. Known adverse events (listed in the table below) are related to their respective trial interventions. These events are secondary outcomes and will be collected as part of the eCRF. The number of occurrences of expected AEs and SAEs will be regularly reviewed throughout the trial by the TMG and the DMC.

Expected AE	Expected SAE
Related to Cochlear Implantation (intervention arm only)	
Facial nerve stimulation (temporary)	Facial nerve stimulation (chronic)
Patient reported decreased hearing ability or loss of residual acoustic hearing (temporary or permanent)	The inability to use the implant or a hearing aid in that ear
Vestibular dysfunction (temporary)	Vestibular dysfunction (chronic)
Perception of non-auditory sensations (temporary or permanent)	Infection requiring hospitalisation (e.g., meningitis and the need for vaccination)
New onset or exacerbation of pre-existing tinnitus	Any surgical complication that requires hospitalisation
Altered taste	Need for revision surgery, reimplantation or explantation
Facial weakness	Subdural injury
Acute otitis media or any other infection treated by oral antibiotics	Chronic pain in or around the implant site or hearing aid
Perilymph fistula	

Expected AE	Expected SAE
Concurrent cerebrospinal fluid (CSF) leakage	
Subcutaneous haematoma	
Unsatisfactory device insertion (e.g., misplacement of electrode array, incomplete electrode insertion, tip fold-over)	
Failure of component parts	
Related to Hearing Aids (intervention and comparator arms)	
Ear infection	None
Exacerbation of eczema	

Serious Adverse Events

A Serious Adverse Event (SAE) is any adverse event occurring following trial mandated procedures that results in any of the following outcomes:

1. Death
2. A life-threatening adverse event
3. Inpatient hospitalisation or prolongation of existing hospitalisation
4. A disability / incapacity
5. A congenital anomaly in the offspring of a participant

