A distinction is drawn between serious and severe AEs. Severity is a measure of intensity whereas seriousness is defined using the criteria above. Hence, a severe AE need not necessarily be serious.

Important medical events that may not result in death, be life-threatening, or require hospitalisation may be considered a SAE when, based upon appropriate medical judgment, they may jeopardize the patient or participant and may require medical or surgical intervention to prevent one of the outcomes listed in this definition.

Events deemed by the investigator to be related to COVID-19 infection will not be reportable.

If an adverse event, *not listed as expected AEs above*, meets, or potentially meets, the SAE criteria it will be assessed for seriousness, and causality.

Causality

Not related or improbable: a clinical event including laboratory test abnormality with temporal relationship to trial device which makes a causal relationship incompatible or for which other treatment, drugs, chemicals or disease provide a plausible explanation. This will be counted as “unrelated” for notification purposes.

Possible: a clinical event, including laboratory test abnormality, with temporal relationship to trial device which makes a causal relationship a reasonable possibility, but which could also be explained by other treatments, devices, drugs, chemicals or concurrent disease. This will be counted as “related” for notification purposes.

Probable: a clinical event, including laboratory test abnormality, with temporal relationship to trial device which makes a causal relationship a reasonable possibility, and is unlikely to be due to other treatments, devices, drugs, chemicals or concurrent disease. This will be counted as “related” for notification purposes.

Definite: a clinical event, including laboratory test abnormality, with temporal relationship to trial device which makes a causal relationship a reasonable possibility, and which can definitely not be attributed to other causes. This will be counted as “related” for notification purposes.

Recording and Reporting of Adverse Events

The below section **does not pertain to** expected AEs and SAEs (included in table of expected events above) which do not require expedited reporting with a trial SAE form. These events are secondary outcomes recorded in medical notes and collected as part of the eCRF, that will be routinely centrally monitored and reported.

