All adverse events (AEs) will be recorded as they are reported whether spontaneously volunteered or in response to questioning about wellbeing at trial visits. The questioning about AEs will cover the current visit as well as the period of time between the previous and the current visit. A note of any concomitant medication will also be made, where available, so that a full assessment of the AE can be made.

Abnormal test results that are deemed clinically significant by the investigator and that lead to a change or temporary or permanent discontinuation in the use of the device or require intervention or diagnostic evaluation to assess the risk to the subject will be recorded as adverse events and instigate further investigation and follow up as appropriate.

All AEs and SAEs will be documented in the subject’s medical records. As both trial interventions are well established and have extensive safety profiles already available, only related, or suspected to be related, SAEs will be documented on the eCRF.

For related, or suspected to be related, events, participants should be followed up until resolution or stabilisation of the event. Follow-up information should ideally be provided on a new SAE form.

Participants will be asked to contact the trial site immediately in the event of any SAEs. The Chief Investigator or nominated deputy shall be informed immediately of any related, or suspected to be related, serious events and shall determine seriousness and relationship in conjunction with any treating medical practitioners.

SAEs will be recorded and reported to the REC and Sponsor as part of the annual progress reports.

SAEs will be reported within the statutory timeframes to the REC as stated below. The Chief Investigator will be responsible for all adverse event reporting.

The NCTU will also notify the trial funder by email from the Chief Investigator to [name] [name], Global Head of Clinical Affairs, Cochlear™ Ltd, [contact] and [name], Clinical Portfolio Manager, Cochlear™ Ltd, [contact] of any serious adverse events at the time of regulatory reporting.

The funder will notify the University by email to [contact] (cc to [contact]) of any reportable events involving devices (Cochlear™ or GN Hearing UK) at the time of reporting to the MHRA, or any other relevant regulatory authorities of any new information which becomes available to them as device manufacturers which could affect the safety of trial participants.

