SAE Reporting Procedure for Unexpected SAEs – At Site

On becoming aware that a participant has experienced an SAE, the Investigator (or delegate) must complete, date and sign an SAE Form. The form should arrive at the NCTU as soon as possible and no later than **24 hours** after first becoming aware of the event:

To report an SAE, email the SAE Form to: [contact]

On receipt, NCTU will allocate each SAE a unique reference number which will be forwarded to the site as proof of receipt. If confirmation of receipt is not received within 1 working day, the site will contact the NCTU. The SAE reference number should be quoted on all correspondence and follow-up reports regarding the SAE and filed with the actual SAE in the ISF.

For SAE forms completed by someone other than the local PI, the Investigator will be required to countersign the original SAE Form to confirm agreement with the causality and severity assessments. For sites where the PI is an audiologist, the responsibility for causality assessment and sign off of SAEs will be delegated to the lead surgeon at site. The form should be returned to NCTU and a copy kept in the ISF.

Investigators should also report SAEs to their own Trust in accordance with local practice.

SAE Reporting Procedure for Unexpected SAE – NCTU

On receipt, NCTU will allocate each SAE a unique reference number which will be forwarded to the site as proof of receipt within 1 working day. The SAE reference number will be quoted on all correspondence and follow-up reports regarding the SAE and filed with the SAE form in the TMF.

On receipt of an SAE Form, seriousness and causality will be determined independently by the Chief Investigator, or their delegate, responsible for determining causality assessments. The Chief Investigator's delegate will review all SAEs reported by the Chief Investigator's host site. An SAE judged by the Investigator, Chief Investigator or their delegate to have a reasonable causal relationship with the trial treatment will be regarded as a related SAE. The Chief Investigator (or their delegate) will also assess all related SAEs for expectedness. If the serious event is unexpected (i.e., is not defined in the protocol as an expected event) it will be classified as an unexpected and related SAE.

SAEs

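### For serious adverse events not on the expected list, causality is defined against the device alone and the unrelated and possible categories overlap, so one event can be coded either way

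*Protocol*

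**What the plan says.** The relevant text is in the protocol's Adverse Events chapter.

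- **Causality.** There are four categories, each worded by timing relative to the trial device. The lowest, *Not related or improbable*, covers an event with a "temporal relationship to trial device which makes a causal relationship incompatible or for which other treatment, drugs, chemicals or disease provide a plausible explanation", and is "counted as “unrelated” for notification purposes". *Possible* covers an event whose timing makes a "causal relationship a reasonable possibility, but which could also be explained by other treatments, devices, drugs, chemicals or concurrent disease", and is counted as related. *Probable* and *Definite* are also counted as related.
- **SAE Reporting Procedure for Unexpected SAE – NCTU.** An SAE judged by the site investigator, the Chief Investigator or the delegate "to have a reasonable causal relationship with the trial treatment will be regarded as a related SAE". The SAEs section after it has the Chief Investigator assess relatedness to the trial intervention.
- **Recording and Reporting of Adverse Events.** For events outside the expected list, "only related, or suspected to be related, SAEs will be documented on the eCRF".
- **Assessment of safety** (Statistics chapter). "Safety data, including number of expected AEs and SAEs and unexpected related SAEs will be summarised with descriptive statistics", by treatment received.

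**The concern.** Two features of the causality text pull against the rest of the chapter.

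The first is the object of causality. The intervention is unilateral cochlear implantation, which is an operation under anaesthesia plus a device. The categories name only the device, and they treat other treatment and drugs as competing explanations. Nothing says that the operation and the anaesthetic are part of what is being judged.

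The second is the overlap. A plausible rival cause is sufficient for the category counted as unrelated. It is also an accepted feature of the lowest category counted as related. No tie-break is given, so two careful raters can follow the text and reach opposite answers.

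For an SAE not on the expected list, that answer decides four things: whether it is documented on the eCRF, whether it counts among the unexpected related SAEs, whether follow-up to resolution or stabilisation applies, and whether it goes to the ethics committee as unexpected and related. Safety is a stated secondary objective. Sites assign these codes while the trial is running, so an analysis plan written later cannot repair them.

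**Working it through.** No arithmetic settles this point. The check sets the definitions side by side and then follows an event coded unrelated.

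**Step 1: which events use the scale.** The Serious Adverse Events section sends an event to causality assessment only if it is not on the expected list and meets, or may meet, the SAE criteria. Listed events are declared related to their interventions and are collected on the eCRF by a separate route. The question is therefore confined to unlisted SAEs.

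**Step 2: the object of causality.**

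| Place | Judged against |
|---|---|
| Causality, all four categories | trial device |
| Unexpected SAE procedure, NCTU | trial treatment |
| SAEs section, Chief Investigator's assessment | trial treatment and trial intervention |

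The two wider terms naturally include the surgery; the first does not say so. The wider terms have no categories of their own, so a rater who needs a definition is sent back to the device wording.

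**Step 3: are the categories exclusive?** Let R mean that a causal relationship is a reasonable possibility, and A that a plausible rival explanation exists. As a simplification, read the first limb of the lowest category as not-R.

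- Lowest category as written: not-R **or** A.
- *Possible* as written: R **and** A.

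| R | A | Category as written | Counted as |
|---|---|---|---|
| yes | yes | lowest category and *Possible* | unrelated and related |
| yes | no | *Probable* or *Definite* | related |
| no | yes | lowest category | unrelated |
| no | no | lowest category | unrelated |

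The first row is the overlap. Simply changing 'or' to 'and' in the lowest category would remove it, but would leave the last row in no category.

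**Step 4: an example.** Take an unlisted SAE shortly after implant surgery that may be due to the anaesthetic. Under the device wording, the anaesthetic can be read as the rival drug, which gives *Not related or improbable*. Because the implant is in place from surgery, the timing also allows *Possible*, defined as a case "but which could also be explained by other treatments, devices, drugs, chemicals or concurrent disease". Under the trial-treatment test it would be related. All three readings come from one chapter.

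**Step 5: what happens if it is coded unrelated.** One positive judgement is enough to make an SAE related, so both the site and the central assessor must say unrelated. The event then stays off the eCRF, is not counted as an unexpected related SAE, and is not sent to the ethics committee under the unexpected-and-related timeframes. It remains in the medical records and on the SAE form, and the protocol also promises SAEs in the annual progress reports.

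**The case against.** The strongest reply is that the chapter has several layers of protection, and most of it stands.

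- The expected list takes many surgical harms off this scale. Among them are facial weakness, CSF leakage, subdural injury, infection needing admission, revision or explantation, and a general entry for surgical complications leading to hospitalisation.
- An unexpected SAE needs a form within 24 hours whatever its relatedness. The central judgement is independent, and either assessor can make the event related. Wording about suspected relatedness pushes borderline cases the same way, and the DMC sees reported SAEs.
- The reference in the SAE definition to "any adverse event occurring following trial mandated procedures" is not a further causality standard. It only fixes which events can be SAEs.
- Treating surgery as another treatment is a strained reading when the intervention is itself cochlear implantation.
- Site staff are unblinded, but the Chief Investigator stays blinded apart from the host site, with unblinding where a causality assessment needs it.

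Two parts of the concern survive. The general entry for surgical complications does not name anaesthetic or general medical events. Whether a post-operative cardiac event, say, is a surgical complication is left to an attribution with no rule. And the overlap in Step 3 does not depend on how surgery is read: it arises for any unlisted SAE with a plausible device cause and a plausible rival.

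**Conclusion.** The definitions need correcting, within a narrow scope. For SAEs off the expected list, the object of causality differs between sections, and an event with both a reasonable causal possibility and a rival explanation fits two categories with opposite consequences.

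A reader might infer that harms of surgery in general, or every event with a rival explanation, would be lost. The protocol does not support that. Listed events bypass the scale, and an unlisted SAE coded unrelated still leaves a record on the SAE form and in the medical notes. The Assessment of safety section also promises the total number and type of AEs and SAEs with no stated relatedness limit. An SAE kept off the eCRF could, however, reach that total only from the SAE form.

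The size cannot be estimated: the protocol gives no rate for such events and no indication of how often both assessors would choose the lower category. For scale only, if all 65 planned for the implant arm are implanted, each omitted participant changes the reported proportion by 1/65, about 1.5 percentage points. Any error would fall mainly on that arm, because only it has surgery, and would tend to understate its harms. The primary outcome is not affected.

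**What to change.** Reword the Causality section and align the reporting sections that follow it.

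1. Use one object throughout: the trial intervention, defined as the device, the implant surgery and anaesthesia, and trial procedures. State that these components do not count as other treatment or drugs.
2. Restrict *Not related or improbable* to events for which a causal relationship is not a reasonable possibility. Say that a plausible rival explanation alone is not enough.
3. Where a causal relationship is a reasonable possibility and a rival explanation also exists, code *Possible*.

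In the terms of Step 3, the lowest category becomes not-R and *Possible* stays R and A, so every row of the table has one outcome and none is left empty.

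The cost is a few sentences, a protocol amendment and a training note for sites and central assessors. Slightly more events will be classed as related and reported. Unlisted SAEs already coded unrelated may need re-assessment under the new wording, which is a reason to change it early.

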Appendix 1: Schedule of Assessments

Measure	Consent	Baseline	Treatment activation (T0) ^c	Time post T0					2,4,5,7,8 months
				1 month	3 months	6 months	9 months		
Primary outcome									
Phoneme perception measured by blinded independent assessors (AB word test @ 60 dBA)		X					X		
Secondary clinical outcomes									
Phoneme perception assessed live by an audiologist (AB word test @ 60 dBA)		X			X	X	X		
Word perception (AB word test @ 60 dBA)		X			X	X	X		
Phoneme perception (AB word test @ 70 dBA)	X						X		
Word perception (AB word test @ 70 dBA)	X						X		
Sentence perception in quiet & noise (BKB sentence test @ 70 dBA)		X			X	X	X		
Device usage (device logging)		X			X	X	X		
Audiometric thresholds (Aided, Unaided)		X	X		X	X	X		
Secondary patient-reported outcomes									
Listening difficulty (SSQ12)		X		X	X	X	X		
Listening effort & fatigue (FAS, EAS, LEQ-CI)		^a X		^a X	^a X	^a X	^a X		
Tinnitus severity (TFI)		X		X	X	X	X		
Tinnitus loudness (VAS-L)		X	^b X	X	X	X	X		
Mood (HADS)		X		X	X	X	X		
Hearing-specific QoL (NCIQ, YBHRQL, HHIA)		X		X	X	X	X		
Health-related QoL (HUI3, EQ5D, ICECAP-A)		X		X	X	X	X		
Global ratings of change				X	X	X	X		
Device usage (self-report)				X	X	X	X	X	
Safety outcomes									
Adverse effects			X	X	X	X	X		
Other assessments									
Cognitive health (HI-MoCA)		X							

^aData for the LEQ-CI to be collected using the LEQ-CI questionnaire once licence is in place. ^bThe VAS-L will be done twice at this timepoint, once immediately before treatment activation and a second time after treatment activation. ^c T0 for HA arm – Either recorded date of HA fitting/optimisation appointment or recorded date of decision that the participant will not attend or 4 months post-randomisation date (whichever occurs first). T0 for CI arm – Either the date of CI activation or the date a decision was made that surgery would not take place.

Appendix 2: Accessories included as part of standard care for processor options

Cochlear™ Nucleus® 7 Kit Unilateral Adult for the Nucleus Profile™ Plus Series Implant (CI600)

1x Processing Unit	2x Standard Rechargeable Battery Modules
1x Earhook M	1x Compact Rechargeable Battery Module
2x Slimline™ Coils (6cm/ 8 cm, each 1)	1x Y Battery Charger
2x Magnets (2(I)/ 3(I), each 1)	1x Charger Plug Pack
2x Microphone Covers (1 pack of 2)	3x Earhooks L (1 pack of 3)
1x Battery Cover	4x Safety Cords (Single/ Double, each 1 pack of 2)
1x Battery Holder	2x Koala Clips
6x power one IMPLANT plus p675 Batteries (1 pack of 6)	3x Snugfit (S/ M/ L, each 1)
1x Battery Cover Locking Tool	3x Earmould Adaptors (1 pack of 3)
1x CR310 Remote Control	1x Bilateral Identification Adhesive Labels
1x Microfibre Cloth	1x Monitor Earphone Adaptor with Earphones
1x Storage Case	
4x Drying Capsules	
1x Breeze by Dry & Store®	
3x Dry-Brik® by Dry & Store® (1 pack of 3)	
1x Recipient Backpack	

[figure not shown]
2x Aqua+ Sleeves (1 pack of 2)	2x Aqua+ Safety Lines (1 pack of 2)
1x Aqua+ Coil (8cm)	4x Microphone Lock Strirrups (1 pack of 4)
1x Activity Kit Case	1x Magnet, Black 3(I)

1x True Wireless™ Device Flyer (to choose 1 of the following: Mini Microphone 2+/ Phone Clip/ TV Streamer)	
---	--

Cochlear Nucleus 8 – Unilateral Adult New System Kit

1x Processing Unit	2x Power Extend Rechargeable Batteries
1x Earhook M	1x Compact Rechargeable Battery
2x Slimline Coils (either 6cm or 8cm)	1x Y Charger
2x Microphone Covers (1 pack of 2)	1x Charger Plug Pack
1x Battery Cover	1x Safety cord (single)
1x Battery Holder	2x Snugfits (1 each M & L)
6x power one IMPLANT plus p675 Batteries	1x Breeze by Dry & Store
1x Battery Locking tool	3x Dry Brik (1 pack of 3)
1x Microfibre Cloth	1x Recipient Backpack
1x Storage Case	1x Mini Mic 2+
4x Drying Capsules	

2x Aqua + Sleeves (1 pack of 2)	2x Aqua+ Safety Lines (1 pack of 2)
1x Aqua + Coil	4x Mic Lock stirrups (1 pack of 4)
1x Activity Case	

Cochlear™ Nucleus® Kanso® Kit Unilateral for the Nucleus Profile™ Plus Series Implant (CI600)

-
- | | |
|---|--|
| 1x Sound Processor | 1x Microphone Protector Kit 2-Pack |
| 1x Magnet 3(I) | 1x Bilateral Identification Adhesive Labels |
| 1x CR210 Remote Control | 1x Magnetic Battery Removal Tool |
| 6x power one IMPLANT plus p675 Batteries (1 pack of 6) | |
| 5x Softwear Pads (1 pack of 5) | |
| 1x Screwdriver and Brush | |
| 1x Microfibre Cloth | |
